#### 9.1.2 Clinical global impression of change

The Clinical Global Impression of Change is a 7-point categorical rating scale in which the investigator assesses the subject's change from Baseline in clinical status.

The number and percentage of subjects for each possible response of the Clinical Global Impression of Change will be presented. In addition, the 3 improvement values (very much improved, much improved, and minimally improved) grouped as “Improved” and the 3 worsening values (minimally worse, much worse, and very much worse) grouped as “Worsened”, as well as the “No change” group will be summarized in the same way. Percentages will be based on the number of subjects with nonmissing values.

### 9.1.3 Caregiver’s global impression of change

The Caregiver’s Global Impression of Change is a 7-point categorical rating scale in which the caregiver assesses the subject’s change from Baseline in clinical status.

The number and percentage of subjects for each possible response of the Caregiver’s Global Impression of Change will be presented. In addition, the 3 improvement values (very much improved, much improved, and minimally improved) grouped as “Improved” and the 3 worsening values (minimally worse, much worse, and very much worse) grouped as “Worsened”, as well as the “No change” group will be summarized in the same way. Percentages will be based on the number of subjects with nonmissing values.

### 9.1.4 Pediatric quality of life inventory

The PedsQL is a validated instrument that consists of generic core scales suitable for use with pediatric populations, including those with acute or chronic health conditions. The PedsQL Measurement Model consists of developmentally appropriate forms for pediatric subjects  $\geq 1$  month to  $\leq 12$  months;  $\geq 13$  months to  $\leq 24$  months;  $\geq 2$  years to  $\leq 4$  years,  $\geq 5$  years to  $\leq 7$  years,  $\geq 8$  years to  $\leq 12$  years, and  $\geq 13$  years to  $\leq 18$  years of age. For each subject, the same version that is used at Visit 2 (Baseline) should be used at Visit 9/ET.

PedsQL generic core scale scores will be calculated for each of the following 4 PedsQL scales:

- Physical Functioning
- Emotional Functioning
- Social Functioning
- School Functioning

The PedsQL assessment is retrospective to the prior 4 weeks, and individual items are scored using a 5-point Likert scale (0 to 4 representing responses of: never, almost never, sometimes, often, or almost always). These scores of 0 to 4 will be transformed by the function:  $100 - (\text{response} \times 25)$  in order to generate scores of 0, 25, 50, 75, and 100 where a higher value represents a better health-related quality of life.

Each scale score is then calculated as the mean of the corresponding nonmissing items if 50% or more of the items are nonmissing. The same algorithm will be used to calculate an overall Total Scale Score (all scales) and the Psychosocial Health Summary Score (a combination of the emotional, social and school functioning questions) for each subject.

Calculated values and change from Baseline for the total scale score and each of the 4 scale scores will be summarized by visit. For the presentation of the PedsQL summary, the questionnaire’s age groups ( $\geq 1$  month to  $\leq 12$  months,  $\geq 13$  months to  $\leq 24$  months,  $\geq 2$  to  $\leq 4$  years,

$\geq 5$  to  $\leq 7$  years,  $\geq 8$  to  $\leq 12$  years, and  $\geq 13$  to  $\leq 18$  years) will be used instead of the ones defined in Section 3.2.5.

### 9.1.5 Health care resource use

To assign the health resources to a specific study period (Baseline, Titration, and Maintenance, respectively), partial or missing dates will be imputed as described for AEs and concomitant medications in Section 4.2.3. Hospital stays will be attributed to study periods based on the admission date.

An event logged on the Hospitalization/ER Visit form of the eCRF where “Emergency room” is marked as initial entry point will be defined as an emergency room (ER) visit. An ER visit with a subject transfer to an inpatient general ward will also be counted as a hospitalization. However, all other instances of ER visits (where subject transfer is not to an inpatient general ward) will not be counted as hospitalizations.

For hospital stays with a discharge date, the duration of each hospital stay will be calculated as the discharge date minus the admission date (Hospitalization/ER Visit Date on the eCRF) plus 1 day. For hospitalizations with either a partial admission or discharge date, the duration of hospital stay will be set to missing. The nonmissing durations of hospital stays will be summed within each of the study periods (Baseline, Titration, and Maintenance, respectively). Should distinct records for hospital stays overlap, then the days during the overlap will only be counted once. Subjects with no hospital stays within a study period will have duration of 0 days for that period. For subjects with hospital stays but no calculable hospital duration, the duration of hospitalization in the respective study period will be missing.

The number of concomitant medical procedures per subject (number of entries in the concomitant procedure form) will be summarized continuously and in categories (0, 1, 2, and 3 or more) for the Baseline Period, the Titration Period, and the Maintenance Period.

The number of healthcare provider consultations per subject will be summarized continuously and in categories (0, 1, 2, 3, 4, and 5 or more) for the Baseline Period, the Titration Period, and the Maintenance Period. In addition, the number and percentage of subjects with at least 1 consultation will be given for general practitioner, specialist physician, nurse, or other by study period.

The number of hospital stays per subject will be summarized continuously and in categories (0, 1, 2, 3, 4, and 5 or more) for the Baseline Period, the Titration Period, and the Maintenance Period. The number and percentage of subjects with specific reasons for a hospital stay (epilepsy, lack of efficacy, AE, elective procedure, and other) will also be summarized for these study periods. Furthermore, the duration of hospital stays will be summarized in categories (0 days, 1 to 5 days, 6 to 10 days, 11 to 15 days, and  $>15$  days) by study period. Descriptive statistics for the number of ER visits within each study period will be presented. These summaries will be repeated by syndrome subgroups (as described in Section 4.8).

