11.2 Serious adverse events

11.2.1 Definition of SAE

Once it is determined that a subject experienced an AE, the seriousness of the AE must be determined. An SAE must meet 1 or more of the following criteria:

- Death
- Life-threatening
(Life-threatening does not include a reaction that might have caused death had it occurred in a more severe form.)
- Significant or persistent disability/incapacity
- Congenital anomaly/birth defect (including that occurring in a fetus)
- Important medical event that, based upon appropriate medical judgment, may jeopardize the patient or subject and may require medical or surgical intervention to prevent 1 of the other outcomes listed in the definition of serious

(Important medical events may include allergic bronchospasm requiring intensive treatment in an emergency room or at home, blood dyscrasias that do not result in inpatient hospitalization, or the development of drug dependency or drug abuse.)

- Initial inpatient hospitalization or prolongation of hospitalization

(A patient admitted to a hospital, even if he/she is released on the same day, meets the criteria for the initial inpatient hospitalization. An emergency room visit that results in admission to the hospital would also qualify for the initial inpatient hospitalization criteria. However, emergency room visits that do not result in admission to the hospital would not qualify for this criteria and, instead, should be evaluated for 1 of the other criteria in the definition of serious [eg, life-threatening adverse experience, important medical event].

Hospitalizations for reasons not associated with the occurrence of an AE [eg, preplanned surgery or elective surgery for a pre-existing condition that has not worsened or manifested in an unusual or uncharacteristic manner] do not qualify for reporting. For example, if a subject has a condition recorded on his/her medical history and later has a preplanned surgery for this condition, it is not appropriate to record the surgery or hospitalization as an SAE, since there is no AE upon which to assess the serious criteria. Please note that, if the pre-existing condition has worsened or manifested in an unusual or uncharacteristic manner, this would then qualify as an AE and, if necessary, the seriousness of the event would need to be determined.)

Hospitalization for the 24-hour ambulatory EEG assessments planned in this protocol will not be considered SAEs.

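### SAP 9.1.5 counts an ER entry as a hospitalization only after transfer to a general ward, so an admission from the ER to intensive care or another unit adds no hospital stay

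*SAP*

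**What the plan says.** SAP 9.1.5 works from the Hospitalization/ER Visit form of the eCRF.

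- **ER visit.** An event for which the emergency room "is marked as initial entry point will be defined as an emergency room (ER) visit".
- **When it also counts as a hospitalization.** "An ER visit with a subject transfer to an inpatient general ward will also be counted as a hospitalization".
- **Everything else.** "However, all other instances of ER visits (where subject transfer is not to an inpatient general ward) will not be counted as hospitalizations".
- **Duration.** For stays with a discharge date, "the duration of each hospital stay will be calculated as the discharge date minus the admission date", plus one day. "Subjects with no hospital stays within a study period will have duration of 0 days for that period". A subject who has stays but none with a calculable duration is set to missing.
- **Outputs per study period.** Number of stays (continuous and in categories), duration in five categories, and the number and percentage of subjects with each reason for a stay. For the ER, "Descriptive statistics for the number of ER visits within each study period will be presented". These are repeated by syndrome subgroup, and SAP 4.8 shows subgroups of 4 or more subjects.

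Protocol 11.2.1, defining a serious adverse event, states: "An emergency room visit that results in admission to the hospital would also qualify for the initial inpatient hospitalization criteria". It names no type of ward. Protocol 4.2 places health care resource use, including hospitalizations, among the preliminary efficacy variables. Protocol 9.4 gives no definition of hospitalization for that purpose.

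**The concern.** The first SAP rule names one destination, and the second closes the category to all others. No exception is made for intensive care, a neurology ward or a monitoring unit. A child who is plainly in hospital can therefore be tabulated as having no stay. Because the zero rule supplies a value, nothing in the stay tables signals that something was left out.

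This population makes the case plausible. Status epilepticus is on the protocol's list of anticipated SAEs (Table 11-1), and Protocol 5.4 gives finding syndromes that LCM might worsen as one purpose of the study. Hospital use by syndrome is a supporting description for that question, and the subgroups may be very small. A definition that depends on which unit received the child, and only when entry was through the ER, is hard to interpret.

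**Working it through.** No figure in the plan depends on this rule, so there is nothing to reproduce. The check is to apply the SAP text to each route into hospital and compare it with Protocol 11.2.1. It assumes one event, no other stay in the period, and no general-ward transfer recorded except where stated.

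| Route | ER visits (SAP) | Hospital stays (SAP) | Duration (SAP) | Reason tabulated | Inpatient hospitalization under Protocol 11.2.1 |
|---|---|---|---|---|---|
| ER, then general ward | 1 | 1 | discharge − admission + 1 | yes | yes |
| ER, then intensive care or other inpatient unit | 1 | 0 | 0 days | no | yes |
| ER, then home | 1 | 0 | 0 days | no | no |
| Direct admission to intensive care | 0 | not excluded by the sentence | discharge − admission + 1 | yes, if counted | yes |

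Two things follow. Rows 2 and 3 are identical in every SAP column, although one child was admitted and the other was not. Rows 2 and 4 may describe the same unit and length of stay, yet only the ER route is excluded.

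**Effect on the duration category.** The dates here are assumed, since the documents contain no hospitalization data. A child enters through the ER on day d, goes to a unit that is not a general ward, and is discharged on day d + 9.

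- Current rule: 0 stays, 0 days, category 0 days.
- If any inpatient admission counted: 1 stay, (d + 9) − d + 1 = 10 days, category 6 to 10 days.
- For assumed stays of 1 to 20 days, the current rule always returns 0 and the changed rule returns 1 to 20. The child therefore moves from the zero category to any of the other four, depending on length.

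**Effect in a subgroup.** With 4 subjects, one reclassified child is 1/4 = 25% of the group in the tables of stays, duration and reasons.

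**Direction.** The same rule applies in the Baseline, Titration and Maintenance Periods. A miss at Baseline makes a treatment period look worse by comparison, and a miss on treatment makes it look better. The sign of any distortion is not fixed.

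**The case against.** The strongest reply is that the rule's effect depends on a form we cannot see. If the transfer field has a single inpatient option, or accepts several transfers, a child who goes from the ER to intensive care and later to a general ward could satisfy the rule. The whole interval from ER date to discharge would then count. That stands: it limits any statement about size, but it does not repair the wording.

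It can also be said that the two definitions serve different purposes, seriousness in the protocol and resource use in the SAP. That is fair. A reader might infer that one report would show the same event as a hospitalization in an SAE table and as no stay here. SAP 8.2.2 tabulates serious TEAEs by system organ class and preferred term, and lists no table by the hospitalization criterion. The inconsistency is between definitions, not between two planned tables.

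Other stronger readings are tempting but not supported:

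- **That the rule hides seizure worsening in a syndrome.** Generalized seizure days (SAP 8.1.2), increases in generalized seizures (9.2) and TEAEs (8.2.2) are all summarized by syndrome. The event also stays in the ER-visit statistics and the data listings (3.1).
- **That the most severe admissions are removed as a class.** Direct admissions to intensive care are not excluded.
- **That mean hospital days would shift by a stated amount.** Duration is planned in categories only, so no mean is affected.
- **That a given percentage of stays is lost.** The documents hold nothing from which to estimate one.
- **That stays without a discharge date become zeros.** If no duration can be calculated, the subject is set to missing. An open stay adds no days unnoticed only when another stay in that period is calculable. Cutting open stays at the end of the period would conflict with the SAP's assignment of stays by admission date.

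**Conclusion.** The point holds as a defect in a stated counting rule. Read literally, SAP 9.1.5 treats an ER entry admitted to any unit other than a general ward as an ER visit alone. It adds no stay and no reason, and it leaves a duration of 0 days when the child has no other counted stay in the period. No other section corrects this.

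The consequence is limited. It touches only the descriptive health care resource use tables (number of stays, duration categories and reasons), overall, by age group and by syndrome. The primary safety variables are untouched. The size rests on two unknowns: the transfer options on the eCRF, and how many children enter through the ER and are admitted elsewhere than to a general ward. It is worth correcting because it yields a wrong count rather than a missing one, and one child can be a quarter of a displayed subgroup.

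**What to change.** Replace the two sentences on ER transfer in SAP 9.1.5 with:

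> An ER visit followed by admission to any inpatient unit (general ward, intensive care or other) is also counted as a hospitalization; ER visits without inpatient admission are not.

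This agrees with Protocol 11.2.1 and treats ER and direct admissions alike. If the sponsor has a reason for the general-ward restriction, the alternative is to state it and tabulate other inpatient admissions from the ER separately.

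The cost is one change of SAP wording and one programming condition. The present rule already relies on a recorded transfer destination, so no new data should be needed. Before finalizing, check that the form's transfer options separate inpatient admission from other outcomes. The rules for duration, missing dates and assignment to study period can stay as they are.

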5.1.1 Study duration per subject

The duration of treatment for an individual subject may be up to approximately 18 weeks excluding the Taper Period.

The study will consist of a 6-week prospective Baseline Period, followed by a 6-week Titration Period and a 12-week Maintenance Period. Subjects may be eligible to enter an additional open-label study (SP848) after completion of the Maintenance Period. Subjects who do not complete the full 12 weeks of the Maintenance Period may still be eligible to enter the SP848 open-label study after consultation with the medical monitor. Subjects who do not continue in the open-label study will enter a 2- to 4-week Taper Period followed by a Safety Follow-Up Visit 2 weeks (±2 days) after the final dose of LCM and a Safety Follow-Up Telephone Contact 30 days (-1/+3 days) after the final dose of LCM. The total study duration for a subject will be up to a maximum of 32 weeks.

The start of the study is defined as the first visit of the first subject entering the study. The end of the study is defined as the date of the last visit of the last subject in the study.

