8 STUDY PROCEDURES BY VISIT

All visits occur at the end of the respective week in the study; a window of ± 2 days relative to Visit 2 is applicable for all visits and telephone contacts.

A detailed tabular schedule of study procedures is provided in Section 5.2.

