### 3.2.3 Study periods

For the purpose of analyses, the following periods are defined.

- Baseline Period:

The Baseline Period is defined as the period of time from the date of Visit 1 to 1 day prior to the date of first dose of LCM. For the definition of Baseline values see Section 3.3.

- Titration Period:

The Titration Period is defined as the period of time from the date of first dose of LCM to the date of Visit 6 or the date of ET, whatever occurs first. If Visit 6 and ET are missing the Titration Period ends at the date of last dose of LCM.

- Maintenance Period:

The Maintenance Period is defined as the period of time from the day after the date of Visit 6 to the date of Visit 9/ET. If Visit 9/ET is missing the Maintenance Period ends at the date of last dose of LCM.

- Treatment Period:

The Treatment Period is defined as the combined Titration and Maintenance Period, ie, starts at the date of first dose of LCM and ends at Visit 9/ET. If Visit 9/ET is missing the Maintenance Period ends at the date of last dose of LCM.

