### 8.1.2 Generalized seizures

Days with any generalized seizures per 28 days (GSD/28d) will be based on the seizure diary and will be derived separately for the Baseline Period, the Titration Period, and the Maintenance Period. Basis for the calculation will be the number of days with at least 1 generalized seizure (GSD) (absence, myoclonic, clonic, tonic, tonic clonic, atonic, partial evolving to secondarily generalized) during the considered study period and the number of days in the considered study period for which seizure information was provided (D):

$$\text{GSD/28d} = \text{GSD} \times (28/\text{D})$$

The days with any generalized seizures per 28 days will only be derived for subjects who completed or discontinued during the respective study period. For subjects who discontinued during the Titration Period, the missing value of the Maintenance Period will be imputed as described in Section 4.2.

Descriptive statistics will be provided for actual values and changes from Baseline for days with any generalized seizures per 28 days by study period. This summary will be repeated by syndrome subgroups (as described in Section 4.8).

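### SAP 9.1.5 tabulates health care resource use as raw totals over periods of about 42, 42 and 84 days, so unchanged use looks higher in Maintenance than at Baseline

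*SAP*

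**What the plan says.** SAP 9.1.5 gives five measures of resource use for Baseline, Titration and Maintenance separately:

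- Medical procedures: the count per subject "will be summarized continuously and in categories (0, 1, 2, and 3 or more) for the Baseline Period" and the two later periods.
- Consultations: "The number of healthcare provider consultations per subject will be summarized continuously and in categories", here running up to 5 or more.
- Hospital stays: a count per subject, also up to 5 or more.
- Hospital days: summed within each period, then "Furthermore, the duration of hospital stays will be summarized in categories" (0, 1 to 5, 6 to 10, 11 to 15, more than 15). A subject with no stay in a period is given 0 days for it, with no condition that the subject entered that period.
- ER visits: descriptive statistics of the number in each period.

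Within a measure the cut-offs are the same for every period. The last paragraph of 9.1.5 repeats its summaries by syndrome subgroup.

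The periods differ in length. Protocol 5.1.1 states: "The study will consist of a 6-week prospective Baseline Period, followed by a 6-week Titration Period and a 12-week Maintenance Period". In SAP 3.2.3, Baseline runs "from the date of Visit 1 to 1 day prior to the date of first dose of LCM" and Maintenance "from the day after the date of Visit 6 to the date of Visit 9/ET", so Maintenance is shorter in subjects who leave early.

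Neither 9.1.5 nor the general rules in SAP 3.1 and 4.2 divide resource use by time in the period. Seizure days are treated differently in SAP 8.1.2: "Days with any generalized seizures per 28 days (GSD/28d) will be based on the seizure diary", scaled by 28 over the number of days with seizure information. SAP 9.1.1 reuses that scaling for each seizure type.

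**The concern.** A count grows with the time over which it is collected. When 6-week and 12-week totals stand side by side, a difference between Baseline and Maintenance mixes any change in use with the longer observation. Early withdrawal pulls the other way, by an amount that depends on retention and on how subjects who never reached Maintenance are counted.

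Protocol 4.2 lists health care resource use among the preliminary efficacy variables, and Protocol 5.4 says the study is meant to identify syndromes with benefit and those where the drug may cause exacerbations. There is no control arm, so the Baseline column is the only reference. A higher Maintenance figure for hospital stays or ER visits could be read as worsening when use is unchanged, and a real reduction could be hidden.

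**Working it through.** The plan gives no figure for this point, so there is none to reproduce.

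**Inputs from the documents.** Baseline 6 weeks = 42 days; Titration 6 weeks = 42 days; Maintenance 12 weeks = 84 days (Protocol 5.1.1). For visit timing, "a window of ± 2 days relative to Visit 2 is applicable for all visits and telephone contacts" (Protocol 8).

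**Assumptions.** The documents give no rate of resource use and no dropout rate. I use 0.1, 0.25 and 0.5 events per 28 days, constant over time, and 0 to 30% leaving in Titration.

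**1. Means in completers.** Expected count = daily rate × days. The rate cancels in the ratio:
- Maintenance / Baseline = 84/42 = 2.0
- Titration / Baseline = 42/42 = 1.0
- With visit windows, Baseline is 40 to 44 days and Maintenance 80 to 88 days, so the first ratio lies between 80/44 = 1.8 and 88/40 = 2.2.

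A true halving of the rate in Maintenance would give 2.0 × 0.5 = 1.0, which looks like no change.

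**2. Dropout.** Let q be the share leaving in Titration and s the share leaving halfway through Maintenance. With zeros kept, ratio = 2 × [(1 − q − s) + 0.5s]. With Titration dropouts excluded, divide by (1 − q).

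| q | s | Zeros kept | Titration dropouts excluded |
|---|---|---|---|
| 0 | 0 | 2.0 | 2.0 |
| 10% | 0 | 1.8 | 2.0 |
| 20% | 0 | 1.6 | 2.0 |
| 30% | 0 | 1.4 | 2.0 |
| 10% | 20% | 1.6 | 1.78 |
| 20% | 20% | 1.4 | 1.75 |
| 30% | 20% | 1.2 | 1.71 |

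**3. Subjects with any use.** In completers under a Poisson model, P(at least 1) = 1 − exp(−mean), with mean = rate × 42/28 at Baseline and rate × 84/28 in Maintenance.

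| Rate per 28 days | Mean, Baseline | Mean, Maintenance | Any use, Baseline | Any use, Maintenance |
|---|---|---|---|---|
| 0.1 | 0.15 | 0.30 | 14% | 26% |
| 0.25 | 0.375 | 0.75 | 31% | 53% |
| 0.5 | 0.75 | 1.50 | 53% | 78% |

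The percentages rise, but not by a factor of 2.

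**4. Hospital days.** A subject with 4 hospital days per 6 weeks has 4 at Baseline and 4 × 84/42 = 8 in Maintenance. The category moves from 1 to 5 days to 6 to 10 days with no change in use.

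**5. After scaling.** Per 28 days, those hospital days are 4 × 28/42 = 2.67 and 8 × 28/84 = 2.67. At 0.5 events per 28 days, raw means of 0.75, 0.75 and 1.50 become 0.50 in all three periods.

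**The case against.** The strongest reply is that the SAP does what the protocol asks. Protocol 13.4.1 requires only descriptive summaries of resource use and defines 28-day scaling only for seizure days. SAP 9.1.5 plans no test, ratio or change from Baseline, whereas seizure days and PedsQL have an explicit change. The period lengths are stated, the variable comes last in Protocol 4.2, and it does not appear in the variable list of SAP 2.2.2.1. No primary or secondary variable depends on it. All of this stands, and it limits the point to interpretation of a lower-tier table.

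It does not remove the point. A reader who knows the period lengths still cannot simply halve the Maintenance column, because the factor changes with retention and with a denominator rule that the section leaves open, and category percentages do not scale by 2.

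Two stronger readings are tempting:

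- A reader might infer that all on-drug use will appear doubled. The documents do not support this. Titration is also on drug and has the same planned length as Baseline. The factor of 2 applies to mean counts in completers. Hospital days are tabulated only in categories, so no doubled mean would be printed for them.
- A reader might infer that the denominator already derived for seizure days can be reused. It cannot: in SAP 8.1.2 it counts days with seizure information, not days in the period.

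A per-subject rate also has faults. One consultation in a subject who leaves on day 7 of a period scores 1 × 28/7 = 4 per 28 days. Because 9.1.5 assigns a whole stay to the period of admission, a long stay starting late in a period could exceed 28 hospital days per 28 days. The fix has to deal with both.

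**Conclusion.** The point holds as one of presentation and interpretation. As written, SAP 9.1.5 places unscaled totals from periods of unequal length side by side. With unchanged use, the expected mean count in Maintenance is about 2.0 times Baseline in completers, whatever the rate, and about 1.8 to 2.2 with visit windows. It is lower where early dropouts are kept as zeros. Category percentages also shift upward, by amounts that depend on the assumed rate.

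The factor of 2.0 rests only on the planned lengths and a constant rate. The category percentages rest on a Poisson model with assumed rates, and the dropout figures on assumed dropout shares. No efficacy or safety conclusion is formally tested on these tables. The change is still worth making because the study has no control arm and the same SAP already scales seizure days over the same periods.

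**What to change.** In SAP 9.1.5, keep the raw count and category tables and add for each measure, by period:

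- A pooled rate per 28 subject-days: total events (or total hospital days) × 28 / total subject-days in the period.
- Subject-days taken from the period start and end dates in SAP 3.2.3.
- Each period restricted to subjects who entered it.
- For this rate only, hospital days counted in the period in which they fall, not the period of admission.

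Per-subject rates may be added, with a note that they are unstable for very short periods. The same rows can go into the syndrome tables.

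The cost is a few SAP sentences and a small amount of extra programming; no new data are needed. The pooled rate removes the effect of period length and of shortened follow-up. It does not remove selection: if subjects who leave use more or less care than those who stay, the Maintenance rate describes those who stayed.
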